11.3 ANALYSIS POPULATIONS

Modified Intent-to-Treat Population

The modified Intent-to-Treat (mITT) population will consist of all randomized participants who receive at least one dose of study drug. This is the primary population for the analysis of the primary endpoint.

The mITT population will be used for tables of demography, baseline characteristics, efficacy and safety.

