Safety Variables	
Safety is a secondary endpoint. The primary safety outcome will be the percent of participants in each arm experiencing AEs.
 
Safety assessments include AEs, Grade ≥ 3 AEs, SAEs, vital sign measurements, clinical laboratory evaluations, and ECGs.
 
Reasons for treatment discontinuation will be documented.
 
Adverse events will be recorded after the ICF/assent form is signed and for 28 days after the last dose of belumosudil.

Pharmacokinetics	Full PK profiles will be collected for approximately 12 participants in each treatment arm at selected sites, and sparse PK sampling will be performed for the whole population, including adolescent participants.
Pharmacodynamics	Samples will be collected for exploratory PD analyses from all participants at sites with appropriate capabilities prior to dosing with belumosudil on Day 1 of Cycles 1, 2 and 7, and upon progression of cGVHD (or flare). PD samples will not be required from adolescents if the site has policies limiting the daily volume of blood allowed to be drawn as part of a clinical trial. Additional samples will be collected from participants enrolled in the site-specific Companion Study for PD analyses as described in Section 21.13 Appendix M .
Statistical Analysis	
Sample Size:
 
Sample size is based on the primary efficacy endpoint of ORR, with a target ORR of 55% and with one planned Interim Analysis (IA). With 63 participants, and a 10% dropout rate, each treatment arm is estimated to have 90% power to yield a 95% confidence interval of ORR that excludes 30%. The Hochberg procedure will be applied for multiplicity adjustment for the primary efficacy endpoint of ORR.
 
Analysis Population:
 
The modified Intent-to-Treat (mITT) population is defined as all participants who are randomized and receive at least one dose of study drug.

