3 INVESTIGATIONAL PLAN

3.1 STUDY DESIGN

This is a Phase 2, randomized, multi-center, open-label, study designed to evaluate the efficacy and safety of belumosudil in participants with active cGVHD after at least 2 prior lines of systemic therapy. The study design is illustrated in [Figure 1](#).

Figure 1 - KD025-213 Study Schema

Participants who consented and/or provided assent documented with a signed an IRB/IEC-approved informed consent/assent form as applicable, and meet all of the eligibility criteria will be enrolled. The study population will be adults and adolescents who:

- Have undergone allogeneic hematopoietic cell transplantation (HCT).
- Have previously received at least 2 lines of systemic therapy for cGVHD.
- Have persistent cGVHD manifestations and systemic therapy for cGVHD is indicated.

A target of $\geq 10\%$ of the enrolled population will have previously received ibrutinib as a therapy for cGVHD.

After confirmation of eligibility during a 14-day screening period, eligible participants will be randomized (1:1) to one of two treatment arms:

- Arm A: belumosudil 200 mg QD
- Arm B: belumosudil 200 mg BID

These doses are selected based upon the data from study KD025-208 ([Section 1.4.1](#)).

Randomization will be stratified according to prior cGVHD treatment with ibrutinib (Yes / No) and severe cGVHD (Yes / No).

With amendment 4, eligible adolescent participants were enrolled into the study at the belumosudil 200 mg QD dose. Since amendment 4, there are no more randomization and stratification factors applied for this group. The additional 20 adults in the companion study will be randomized (1:1) to Arm A or Arm B. The expected sample size in each Arm is therefore: Arm A, N = 93 with addition of 20 adolescents and 10 adults and Arm B, N = 73 with addition of 10 adults. Any adolescent taking a PPI or a strong CYP3A4 inducer will begin C1D1 at the following escalated dose: belumosudil 200 mg BID.

Concomitant treatment with standard of care systemic cGVHD therapies such as calcineurin inhibitors (tacrolimus, cyclosporine), sirolimus, MMF, methotrexate, rituximab or extracorporeal photopheresis (ECP), are permitted as long as the participant has been on a stable dose / regimen of these per the eligibility criteria. Initiation of new systemic cGVHD therapy while on study is not permitted.

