Participants will receive belumosudil treatment in 28-day cycles until clinically significant progression of cGVHD (defined as progression requiring addition of new systemic therapy for cGVHD), histologic recurrence of underlying malignancy, unacceptable toxicity, Investigator decision, participant preference / withdrawal of consent, lost to follow-up, sponsor decision, or death (whichever occurs first).

Participants who experience cGVHD progression as defined by NIH criteria but for whom no new systemic therapy is planned may continue to receive belumosudil and be assessed again at their next cycle. If progression per NIH criteria is not confirmed or no new systemic therapy is planned, participants may continue on belumosudil per investigator discretion until they fulfill one of the criteria requiring discontinuation of study drug.

Under Protocol Amendment 3, all participants (excluding the 20 adolescent participants) that have received at least 6 months of belumosudil treatment or are in long-term follow-up without having a failure-free survival event are expected to end participation in study KD025-213. Participants may continue to participate in study KD025-213 if the Investigative Site is awaiting IRB approval of the KD025-217 rollover study titled: “Extended Treatment and Follow-up of Participants Treated with Belumosudil in Study KD025-208 or Study KD025-213”.

The primary endpoint is the overall response rate (ORR), defined as the proportion of participants achieving a partial response (PR) or a complete response (CR) as defined by the 2014 NIH Consensus Development Project on Clinical Trials in cGVHD ([Appendix B](#)). Response criteria will be assessed after Cycles 1, 2, 3 and 4 and then after every other Cycle thereafter (Day 1 of Cycles 2, 3, 4, 5, 7, 9, 11, etc.) ([Table 6](#)). Following Protocol Amendment 5, in adolescent participants still to be enrolled, response criteria will be assessed after Cycles 1, 2, 4, and 6 and then after every third cycle (Day 1 of cycles 2, 3, 5, 7, 10, 13, etc.). Responses are assessed with respect to baseline.

Analyses of the primary endpoint will be participant to multiplicity adjustment per a Hochberg procedure ([Section 11.2.1](#)).

Secondary endpoints will include assessments to evaluate the clinical meaningfulness of responses. These include duration of response, changes in Lee Symptom Scale Scores, response by organ system and changes in corticosteroid dosage.

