6.4 SAFETY

6.4.1 Safety Endpoints

Safety is a secondary endpoint. The primary safety outcome will be the percent of participants in each arm experiencing AEs. See below and [Section 9](#) for additional details.

- Adverse Events and SAEs.
- Hematological and clinical chemistry parameters.
- Vital signs.
 - Change from baseline in systolic blood pressure, diastolic blood pressure and heart rate.
- 12-Lead ECG
 - Mean and maximum change from baseline in QTc(F).

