11 STATISTICAL CONSIDERATIONS

Three analyses are planned:

1. An interim analysis (IA) will be conducted approximately 2 months after 126 participants have been enrolled into the mITT population. A nominal 1-sided alpha of 0.0025 will be spent, but there will be no early study termination for efficacy.
2. The primary analysis (PA) will be conducted approximately 6 months after 126 participants have been enrolled into the mITT population, with 1-sided alpha 0.0225 (or 0.025 if the ORRs of both arms are significant at interim).
3. A follow-up analysis will be conducted approximately 12 months after 126 participants have been enrolled into the mITT population.

Additional analyses will be conducted to include adolescent participants and Companion Study participants, approximately 6 months after completion of enrollment of the respective participants.

Alpha will only be allocated to the primary endpoint, ORR.

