11.9 SAFETY ANALYSES

Safety is a secondary endpoint.

Treatment exposure will be summarized.

Safety analyses include:

- Adverse Events and SAEs
 - Treatment-emergent AEs will be summarized by treatment group using MedDRA® (Version 20.0 or greater) System Organ Class (SOC) and preferred term, classified from verbatim terms. The incidence and percentage of participants with at least 1 occurrence of a preferred term will be included. Causality (relationship to study treatment) will be summarized separately.
 - AEs, SAEs, related AEs, related SAEs, \geq Grade 3 AEs, related \geq Grade 3 AEs, and AEs leading to withdrawal, or treatment discontinuation will be summarized overall and by treatment arm. AEs will also be presented in listings. Duration of AEs will be determined and included in listings, along with action taken and outcome.
- Hematological and clinical chemistry parameters using central laboratory
 - Laboratory results will be classified using CTCAE v5.0 and summarized by treatment arm. Incidence of laboratory abnormalities will be summarized. The worst on-study grade after the first dose of study drug will be summarized. The incidence of \geq Grade 3 laboratory abnormalities under treatment and shifts in toxicity grading from baseline to highest grade post-baseline will be displayed.
- Vital signs
 - Change from baseline in systolic blood pressure, diastolic blood pressure and heart rate will be presented.
- 12-Lead ECG
 - Mean and maximum change from baseline in QTc(F) will be derived.

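### Protocol 11.3 defines only a randomized-and-dosed population and assigns it to the safety tables, so adolescents dosed without randomization since Amendment 4 fall outside the later AE tables and the 12-17 subgroup as written

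*Protocol*

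**What the plan says.** Protocol 11.3 has one population, mITT, which "population will consist of all randomized participants who receive at least one dose of study drug". It then says what the set is for: "The mITT population will be used for tables of demography, baseline characteristics, efficacy and safety". The synopsis gives the same definition: the mITT "population is defined as all participants who are randomized and receive at least one dose of study drug". Section 11.7.1 also takes the ORR denominator from mITT.

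Section 3.1 describes how adolescents now enter the study. They are enrolled directly at one regimen: "Since amendment 4, there are no more randomization and stratification factors applied for this group". It also sets an assessment schedule that begins "Following Protocol Amendment 5, in adolescent participants still to be enrolled", so under the current version more such participants were expected. The same section counts the 20 added adolescents in Arm A, giving expected sizes of 93 and 73.

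On reporting, 6.4.1 states: "The primary safety outcome will be the percent of participants in each arm experiencing AEs". Section 11.9 says that the adverse event categories "will be summarized overall and by treatment arm", and names no population. Section 11.4 lists an age subgroup of 12-17. Section 11 adds: "Additional analyses will be conducted to include adolescent participants and Companion Study participants". It does not say which analysis set those analyses use.

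The SAP supplied (version 2.1) does not fill the gap. Its safety population in 3.4 is again limited to randomized, dosed subjects and is declared equivalent to mITT. Section 2.3 plans about 126 subjects, and the age subgroup in 3.8.4 splits only at 65.

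**The concern.** A dosed adolescent who was never randomized cannot meet the 11.3 definition, yet 11.3 is the only rule that says who goes into the safety tables. The definition was not updated when Amendment 4 stopped randomizing adolescents.

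The primary safety outcome is a percentage within each arm, so its denominator has to be unambiguous. A programmer who follows 11.3 leaves treated minors out of the adverse event tables. One who follows the head count in 3.1 puts them in, by a rule that is not written down. The two would report different Arm A denominators for the same table in the later analyses. The 12-17 subgroup has the same problem. These are the tables in which adolescent safety would be read, and Protocol 1.6 says the study may further inform the prescribing information.

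**Working it through.** **Step 1. Reproduce the plan's head count.** Inputs: about 126 participants before the expansion, 63 per arm (Protocol 11.2 and 4.1); 20 Companion Study adults randomized 1:1, so 10 per arm (3.1); 20 added adolescents, all counted in Arm A (3.1).

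- Arm A: 63 + 10 + 20 = 93
- Arm B: 63 + 10 = 73
- Total: 93 + 73 = 166, which equals 126 + 20 + 20

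These match 3.1 and the synopsis exactly.

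**Step 2. Apply the 11.3 definition.** Two conditions must both hold.

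| Group | Randomized? | Dosed? | In mITT as written? |
|---|---|---|---|
| First 126, any age | Yes | Yes | Yes |
| Companion Study adults | Yes | Yes | Yes |
| Adolescents randomized before Amendment 4 | Yes | Yes | Yes |
| Adolescents enrolled since Amendment 4 | No | Yes | No |

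**Step 3. Look for another rule that brings the last group back.** Section 11.9 names no population. Section 11.4 names none either, so the subgroup inherits mITT from 11.3 (efficacy and safety tables) and 11.7.1 (ORR). Section 11 announces adolescent analyses without a set. Section 11.5 defers to the SAP, and the SAP supplied repeats the restriction to randomized subjects. No rule brings them back.

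**Step 4. Size.** Let m be the number of added adolescents who were not randomized. The documents do not give m. Section 3.1 says that some were enrolled this way and that others were still to be enrolled, so by plan m is above 0; the upper limit is 20. Assuming everyone counted is dosed:

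- mITT total read literally = 166 - m
- Share of all participants left out = m / 166

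| m | Total as written | Total, all dosed | Share left out |
|---|---|---|---|
| 5 | 161 | 166 | 5/166 = 3.0% |
| 10 | 156 | 166 | 10/166 = 6.0% |
| 20 | 146 | 166 | 20/166 = 12.0% |

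For Arm A, only m = 20 follows from stated figures, because 93/73 places none of the 20 added adolescents in Arm B: 93 - 20 = 73 as written against 93 dosed, a loss of 20/93 = 21.5%. For smaller m the arm split depends on how any earlier-randomized adolescents were allocated. The documents do not say, so no intermediate arm figure is claimed.

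**The case against.** The strongest reply is that the intent is plain. Section 11 schedules analyses that include adolescents, 3.1 counts them in Arm A, and the safety outcome is defined per arm. On this view a programmer who dropped them would be contradicting the plan, and the defect is one outdated word. The intent is conceded. It does not supply a denominator: the only stated rule still excludes these participants, and the plan names no other set.

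The reply on consequence largely stands. The interim, primary and follow-up analyses are all timed from 126 mITT participants, and the adolescents have their own later analyses. Approval on this study's data is dated July 2021 (Protocol 1.6), whereas Amendment 4 is dated April 2022 (Appendix O). A reader might infer that the primary ORR result or the data behind that approval are compromised. The documents do not support that.

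Two other stronger readings fail as well. One is that adolescent safety data are lost: Section 9.3.2.1 collects all adverse events from consent onward, so this is a table denominator only. The other is that the 12-17 subgroup would be empty: Amendment 1 had already lowered the age limit to 12, so adolescents randomized before Amendment 4, including any among the first 126, remain in mITT.

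A reader might also press the lack of a rule on whether adolescents counted in Arm A who start at 200 mg BID are tabulated by arm label or by starting regimen. Section 3.1 puts both statements in one paragraph and 11.9 tabulates by arm, so the arm label is the natural reading. At most this needs a clarifying sentence. Finally, a later SAP may exist that defines the adolescent set. That cannot be checked here, and the protocol wording would still need correcting.

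**Conclusion.** The point holds. As written, the only defined population, which 11.3 assigns to the safety tables, excludes participants whom the protocol itself treats, counts in Arm A and plans to analyze. The number is above 0 by plan and at most 20. At the limit, which is also the case consistent with the 93/73 count, Arm A falls from 93 to 73 and the total from 166 to 146.

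This assumes that the planned numbers are reached, that all those counted are dosed, and that 11.3 is read literally. The effect is confined to descriptive safety, adolescent and age-subgroup tables in the later analyses that include the added adolescents. The change should be made, but it does not bear on the confirmatory result.

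**What to change.** - In Protocol 11.3 and the synopsis, define a safety population of all participants who receive at least one dose of belumosudil, randomized or not, and assign the safety tables to it.
- State in Section 11 and 11.4 that the additional adolescent analyses and the 12-17 subgroup use all dosed adolescents, with the non-randomized ones flagged, and report how many there are.
- Keep the randomized mITT for the per-arm ORR test.
- Carry the same definitions into the SAP in place of the safety population in its 3.4, in a version that covers the expansion.
- As housekeeping, reconcile 4.1 (about 83 per arm) and 5.2 and 5.3 (all participants randomized) with 3.1. Also remove or define the ITT population that the synopsis names for demographics.

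The cost is wording in the protocol and SAP and one flag in the tables. It needs no new data, changes nothing in treatment, and does not affect the primary test.

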11.4 SUBGROUP ANALYSES

Subgroup analyses will be conducted for the following subgroups:

- Prior ibrutinib (Yes / No).
- Severe cGVHD (Yes / No).
- Number of organs involved (<4 / \geq 4).
- Number of prior lines of therapy (\leq 3 / $>$ 3).
- Duration of cGVHD before enrollment.
- Lung involvement (Yes / No).
- Concomitant treatment with a proton pump inhibitor (Yes / No).
- Age (12-17, 18-64, \geq 65).

11.5 DATA ANALYSIS

All pre-specified analyses will be described in a Statistical Analysis Plan (SAP).

11.6 INTERIM ANALYSIS

Interim, primary, and follow-up analyses are described above.

Ongoing monitoring of safety data will be conducted in accordance with study stopping rules ([Section 10](#)).

11.7 EFFICACY ANALYSES

11.7.1 Primary Efficacy Endpoint

The ORR is defined as the proportion of participants (from the mITT population) meeting the overall response criteria assessment of complete or partial responses at any post-baseline response assessment ([Section 6.3.2](#)).

11.7.2 Secondary Efficacy Endpoints

Secondary endpoints are as follows:

- Duration of response (DOR): Assessments of DOR will include:
 - The time from initial response of PR or CR until documented progression from best response of cGVHD, new cGVHD therapy, or death.
 - Time from initial response to start of additional systemic cGVHD therapy or death.
- Changes in the Lee Symptom Scale Score: Analyses will include:
 - Number of participants with a ≥ 7 point reduction.
 - Number of participants with a ≥ 7 point reduction on 2 consecutive assessments.
 - Duration of a ≥ 7 point reduction.
- Response by organ system: The response assessment for the nine individual organs (Skin, Eyes, Mouth, Esophagus, Upper GI, Lower GI, Liver, Lungs, and Joints and fascia).
- Time to response (TTR): defined as the time from the first dose of belumosudil to the first documented cGVHD response.
- Time to next therapy (TTNT): defined as the time from the first dose of belumosudil to the start of additional systemic cGVHD therapy.
- Number and percentage of participants who have a best response of PR and number and percentage of participants who have a best response of CR.
- Change in corticosteroid dose:
 - The prednisone equivalent dose of corticosteroids (mg/kg/day) during the study will be analyzed ([Appendix K](#)).
- Change in calcineurin inhibitor dose.
- Failure-free-survival (FFS): FFS is defined as the absence of cGVHD treatment change, non-relapse mortality and recurrent malignancy ([Section 6.3.5](#)). Median FFS (from first dose of belumosudil) and landmark FFS at 1 year will be analyzed.
- Overall survival (OS): Defined as time from first dose of belumosudil to the date of death due to any cause.
- Changes in cGVHD global severity rating using the Clinician-Reported Global cGVHD Activity Assessment.

- Changes in symptom activity using the cGVHD Activity Assessment Patient Self-Report.

Descriptive statistics will be provided for all secondary endpoints.

11.8 EXPLORATORY ANALYSES

- Changes in the PROMIS Global Health subscores for physical and mental functioning.
- ORR using Kadmon Algorithmic Response Assessment (KARA) for overall response.
- Changes in the expression of relevant biomarkers after belumosudil administration ([Section 11.11](#)).

11.9 SAFETY ANALYSES

Safety is a secondary endpoint.

Treatment exposure will be summarized.

Safety analyses include:

- Adverse Events and SAEs
 - Treatment-emergent AEs will be summarized by treatment group using MedDRA® (Version 20.0 or greater) System Organ Class (SOC) and preferred term, classified from verbatim terms. The incidence and percentage of participants with at least 1 occurrence of a preferred term will be included. Causality (relationship to study treatment) will be summarized separately.
 - AEs, SAEs, related AEs, related SAEs, \geq Grade 3 AEs, related \geq Grade 3 AEs, and AEs leading to withdrawal, or treatment discontinuation will be summarized overall and by treatment arm. AEs will also be presented in listings. Duration of AEs will be determined and included in listings, along with action taken and outcome.
- Hematological and clinical chemistry parameters using central laboratory
 - Laboratory results will be classified using CTCAE v5.0 and summarized by treatment arm. Incidence of laboratory abnormalities will be summarized. The worst on-study grade after the first dose of study drug will be summarized. The incidence of \geq Grade 3 laboratory abnormalities under treatment and shifts in toxicity grading from baseline to highest grade post-baseline will be displayed.
- Vital signs
 - Change from baseline in systolic blood pressure, diastolic blood pressure and heart rate will be presented.
- 12-Lead ECG
 - Mean and maximum change from baseline in QTc(F) will be derived.

11.10 PHARMACOKINETIC ANALYSES

The pharmacokinetic profile of belumosudil and major metabolites will be evaluated. Further details will be described in the Pharmacokinetic Analysis Plan.

11.11 PHARMACODYNAMIC ANALYSES

Further details will be described in the Pharmacodynamics Analysis Plan.

12 DATA QUALITY ASSURANCE

Accurate and reliable data collection will be ensured by verification and cross-check of the eCRFs against the Investigator's records by the study monitor (source document verification) and by the maintenance of a drug-dispensing log by the Investigator. Collected data will be entered into a computer database and participant to electronic and manual quality assurance procedures.

